9. Participation in another therapeutic investigational drug trial in which administration of an investigational study medication occurred within 30 days prior to Visit 1.

Duration of Treatment

The duration of the study participation is anticipated to be a maximum of 124 days per subject. The final visit (Visit 8) has a maximum allowable visit window of 14 days: Study visits are:

- Visit 1 (Day -13 to 0) screening
- Visit 2 (Day 1) randomization; study medication treatment
- Visit 3 (Day 8) follow up visit
- Visit 4 (Day 22) follow up visit; Target Lesions that meet the retreatment criteria will receive a second study medication treatment
- Visit 5 (Day 29) follow up visit
- Visit 6 (Day 50) follow up visit
- Visit 7 (Day 78) follow up visit
- Visit 8 (Day 106) follow up visit; end of study

Criteria for Evaluation

Efficacy:

The investigator will evaluate the severity of each SK Target lesion using the Physician's Lesion Assessment (PLA)

Safety:

Safety will be evaluated by following adverse events, clinical laboratory exams, vital signs, concomitant medications, as well as through skin examinations and general physical exams.

Study Drug Administration

Study drug medication will be applied to each of the four Target Lesions during Visit 2 by the treating physician or a member of the investigational site staff who is a trained healthcare professional.

Study medication must be applied to each of the Target Lesions for approximately 20 seconds. Each Target Lesion will be treated up to 4 times while waiting approximately 60 seconds between each application.

Study medication must be applied to a total of 4 SK Target Lesions. At least one of the SK Target Lesions must be on the face and at least one must be on the trunk or extremities.

Statistical Methods*Efficacy Analysis*

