3.2.2. Secondary Objective

The secondary objectives of this study include:

- Duration of response
- Safety of A-101

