4. STUDY DESIGN

This is a phase 2, randomized, multi-center, study designed to evaluate the safety and efficacy of A-101 45% compared to A-101 40% and each active treatment arm to Vehicle in subjects with seborrheic keratosis lesions.

During the study, the investigator will identify 4 eligible SK Target Lesions on each subject on the trunk, extremities and face. For each subject, at least 1 SK Target Lesion must be on the face and at least 1 Target Lesion must be on the trunk or extremities. The Target Lesions will be treated at a maximum of two treatment visits.

Subjects will be required to complete a total of 8 study visits. The protocol defined study visits are:

- Visit 1 (Day -13 to 0) Screening
- Visit 2 (Day 1) Subject randomization and study drug application
- Visit 3 (Day 8) Target Lesion assessment
- Visit 4 (Day 22) Target Lesion assessment and if a Target Lesion meets the retreatment criteria the subject will receive a second study drug application
- Visit 5 (Day 29) Target Lesion assessment
- Visit 6 (Day 50) Target Lesion assessment
- Visit 7 (Day 78) Target Lesion assessment
- Visit 8 (Day 106) Target Lesion assessment and end of study visit

Refer to Section 6 or a complete list of protocol required study assessments.

A completed evaluable subject is a subject that completes all required treatment Visits (Visit 1 and Visit 4), completes Visit 8 (end of study visit), has had all Target Lesions assessed at these visits and has not had a protocol violation documented during the study

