4.2. Duration of Study

The anticipated time for study enrollment is 4 months. The duration of study participation is anticipated to be a maximum of 124 days per subject. Subjects will have a total of 8 study visits. The maximum anticipated duration for the study is approximately 8 months.

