8.1.2. Physician's Lesion Assessment (PLA)

The PLA is the investigator's assessment of the severity of the Target Lesion at a particular time point. The investigator should NOT refer to any other assessments to assist with these assessments.

At Visits 1, 2, 4, 6, 7 and 8, the investigator will assess the Target Lesion using the scale below and report the one integer that best describes the severity of the Target Lesion. At Visit 2, and if appropriate Visit 4, the investigator must complete the PLA prior to the study medication treatment.

Table 3 Physician's Lesion Assessment Definitions

Physician's Lesion Assessment	
Grade	Descriptor
0	Clear: no visible seborrheic keratosis lesion
1	Near Clear: a visible seborrheic keratosis lesion with a surface appearance different from the surrounding skin (not elevated)
2	Thin: a visible seborrheic keratosis lesion (thickness ≤ 1 mm)
3	Thick: a visible seborrheic keratosis lesion (thickness > 1 mm)

All investigational site staff will receive training on the PLA Assessment Scale and be provided with a PLA Assessment Manual (refer to Appendix 15.2) that will be used as a reference tool during the conduct of the study.

In order for a subject to be eligible for screening and randomization to the study, each Target Lesion must have a PLA grade of ≥ 2 .

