Duration of response will be calculated on a lesion basis by determining the percentage of clear lesions (PLA=0) at Visit 8 which remain clear at Visit 13. This will be done for each treatment group separately.

For all analyses, two-tail alpha will be set to 0.05 with no adjustment for multiple comparisons. ANOVAs will include Site in the model if doing so improves the sensitivity of the model for comparing treatment groups.

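### Duration of response, a secondary objective, is defined on a Visit 13 that this trial does not have, so it cannot be calculated as written

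*Combined protocol and SAP*

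**What the plan says.** Section 3.2.2 names "Duration of response" first among the secondary objectives, and the synopsis lists it too. The method is in Section 12.2: a lesion-level percentage, reported separately for each treatment group, obtained by "determining the percentage of clear lesions (PLA=0) at Visit 8 which remain clear at Visit 13". No other section defines it.

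The schedule is stated several times and always stops at Visit 8:

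- Section 4: "Subjects will be required to complete a total of 8 study visits", the last being "Visit 8 (Day 106) Target Lesion assessment and end of study visit".
- Synopsis: "Visit 8 (Day 106) follow up visit; end of study".
- Section 4.2: "Subjects will have a total of 8 study visits", and "The duration of study participation is anticipated to be a maximum of 124 days per subject".
- Section 8.1.2, on when the PLA is scored: "At Visits 1, 2, 4, 6, 7 and 8, the investigator will assess the Target Lesion using the scale below".
- Section 6, Table 1: columns V1 to V8 only.

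**The concern.** The definition compares two assessments of the same lesion, and the second belongs to a visit outside the schedule. If the sentence is followed literally, every lesion in the denominator has a missing outcome and the objective cannot be reported.

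The data that are collected would support several replacement definitions, which start from different visits, cover different lengths of follow-up and select different lesions. They can give different percentages. The documents do not choose among them. If the choice is left until treatment-level results are known, the reported durability figure is open to the criticism that it was selected after the event.

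**Working it through.** The plan attaches no numerical target to this endpoint, and its power statement (Section 12.1) does not cover it. The check is therefore of the definition against the schedule.

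**1. What the definition needs.** PLA at Visit 8 for the denominator, and PLA at Visit 13 for the numerator.

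**2. What is collected.** PLA visits and nominal days, from Section 8.1.2 and Table 1:

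| Visit | Nominal day | Window (days) |
|---|---|---|
| 1 | −13 to 0 | none |
| 2 | 1 | none |
| 4 | 22 | +4 |
| 6 | 50 | ±7 |
| 7 | 78 | ±7 |
| 8 | 106 | ±7 |

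There are 0 scheduled PLA assessments after Visit 8.

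**3. Could a later visit be implied?** Day −13 to Day 106, counting Day 0, is 14 + 106 = 120 days. The stated maximum participation of 124 days leaves 124 − 120 = 4 days, less than Visit 8's own +7-day window. No extension phase is described. The Visit 12 (Day 148) in Section 2.2.3 belongs to the separate open-label study A-101-SEBK-303.

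**4. Is it only a wrong visit number?** No. The starting point is Visit 8, already the last PLA, so no value put in place of 13 gives a later assessment.

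**5. How many lesions are affected?** The upper bound is 250 subjects × 4 lesions = 1,000. The true denominator is the subset with PLA = 0 at Visit 8. The number with an observable outcome is 0 in either case.

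**6. What could be calculated instead?** Intervals from each post-baseline PLA visit to Visit 8, nominal and with the windows at their extremes:

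| Start | Nominal interval | Shortest | Longest |
|---|---|---|---|
| Visit 4 | 106 − 22 = 84 days | 99 − 26 = 73 | 113 − 22 = 91 |
| Visit 6 | 106 − 50 = 56 days | 99 − 57 = 42 | 113 − 43 = 70 |
| Visit 7 | 106 − 78 = 28 days | 99 − 85 = 14 | 113 − 71 = 42 |

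Under Section 7.5 only lesions with PLA above 0 can be re-treated at Visit 4. A Visit 4 start therefore selects lesions that cleared after one treatment. Visit 6 is the first PLA after the last possible treatment, since none is scored at Visit 5.

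**The case against.** The contradiction itself has no good defence, but four points can fairly be made about its weight and the remedy.

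- **The damage is confined.** The endpoint is a per-arm percentage with no between-arm test. The primary analysis, the PLA ≤ 1 analysis and the responder analyses all use Visit 8 data and stand as written. Section 12.2 also repeats the clearance analyses at the other PLA visits. This is correct, but those are cross-sectional percentages and do not show whether a lesion that cleared stayed clear.
- **A post hoc definition is not inevitable.** The trial is double-blind, no interim analysis is planned (Section 12.4), Section 13.1 provides for amendments, and the database is locked before analysis (Section 13.5). This stands: the risk arises only if the text is not corrected before unblinding.
- **1,000 lesions overstates the scale.** This also stands. As a rough guide, assume the 28.2% mean clearance reported for study 303 (open-label, up to four applications, per-protocol population). The two active arms would then supply about 200 × 4 × 0.282 ≈ 226 clear lesions. Vehicle would add few: no vehicle subject in studies 301 or 302 cleared three or more of four lesions.
- **A Visit 6 start changes the question.** The written definition asks what happens after Day 106. A definition on collected visits asks what happens up to Day 106 and omits lesions that first clear at Visit 7 or 8. Only added follow-up would keep the written question. This is a real limitation, to be stated when the choice is made.

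**Conclusion.** The concern holds. The only specified analysis of a stated secondary objective cannot be computed for any lesion in any arm, and correcting the visit number alone would not rescue it. It needs to be fixed because an objective has no workable analysis, not because the main efficacy conclusion is in doubt.

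The conclusion rests on the visit and PLA schedules as printed, which agree with each other throughout, and on the absence from the supplied documents of any later follow-up or alternative definition. It depends on no assumed rate. How far the candidate definitions would differ in their results cannot be estimated, because the documents give no recurrence data.

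**What to change.** Amend Section 12.2 before unblinding. One definition that works with the existing schedule:

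> Duration of response will be summarised by lesion in the per-protocol population as the percentage of target lesions with PLA = 0 at Visit 6 that also have PLA = 0 at both Visit 7 and Visit 8, by treatment group, with a 95% confidence interval allowing for clustering of lesions within subject. This describes recurrence up to Day 106 only.

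State how a missing Visit 7 PLA is handled, and report numerators and denominators, since the vehicle denominator may be too small for a useful interval. The clustered interval is a refinement, wanted because one subject can contribute up to four lesions; the defect is cured without it.

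A Visit 4 or Visit 7 start is also computable. The sponsor should choose one and give the reason. If durability beyond Day 106 is what matters, PLA follow-up after Visit 8 would have to be added to the schedule and the participation limit revised.

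The amended sentence needs no new visits, subjects or procedures. Its cost is that durability is described over a nominal 56 days (42 to 70 with the windows), and that lesions first clearing at Visit 7 or 8 are left out. If the data are already unblinded, whichever definition is used should be labelled post hoc.

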1. SYNOPSIS

Protocol Number A-101-SEBK-204 Synopsis	
Protocol Number:	Protocol Title: A Phase 2 Randomized, Double-Blind, Vehicle-Controlled, Parallel Group Study of the Safety and Effectiveness of A-101 (hydrogen peroxide) Topical Solution in Subjects with Seborrheic Keratosis Lesions on the Trunk, Extremities and Face
Sponsor: Aclaris	Phase of Development: Phase 2
Study Drug Description: A-101 Solution (40% and 45%) is a hydrogen peroxide solution that will be supplied in a glass ampule with an applicator to be applied to seborrheic keratosis lesions of the trunk, extremities and face.. The study drug, A-101 (hydrogen peroxide) 40% and 45% Topical Solution (hereafter referred to as A-101) is a colorless solution that must be stored at room temperature (20-25° C or 68 -77 ° F), protected from light.	
Study Objectives: Primary: The main objective of this study is to evaluate the effectiveness of A-101 40% and A-101 45% versus vehicle for the treatment of 4 seborrheic keratosis (SK) Target Lesions on the trunk, extremities and face. Secondary: The secondary objectives of this study include: 
 • Duration of response • Safety 	
Study Design: This is a phase 2, multicenter, randomized study to evaluate the safety and efficacy of A101 40% and A101 45% versus vehicle. Subjects will be required to have a total of 4 target seborrheic keratosis (SK) lesions located on their trunk, extremities and face. At least one of the 4 target lesions must be on the face and at least one of the target lesions must be on the trunk or extremities. Subjects will be randomized to one of 3 treatment arms in a 1:2:2 ratio. Fifty subjects will be randomized to the Vehicle treatment arm and 100 subjects will be randomized to each A-101 active treatment arm. Subjects will receive a maximum of 2 treatments [Day 1 (Visit 2) and re-treatment on Day 22 (Visit 4) if a target lesion meets the criteria for re-treatment]. The duration of study participation is anticipated to be up to a maximum of 124 days per subject. Safety will be evaluated based on clinical laboratory studies (hematology and clinical chemistry), vital signs, assessment of local skin reactions (LSRs), assessment of adverse events (AEs), and concomitant medication review.	

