12. STATISTICAL CONSIDERATIONS

12.1. Sample Size and Power Consideration

Based on results from a previous study with similar design, the expected standard deviation for the primary efficacy parameter is approximately 23.7%. The mean difference between the two Active treatment groups is expected to be approximately 10 percentage points. With approximately 250 randomized subjects this study is expected to achieve approximately 85% power for the comparison between the two Active treatment groups, and more than 95% power for the pair-wise comparisons between each Active treatment group and the Vehicle group. Two-tail alpha will be set to 0.05 for all comparisons.

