12.2. Statistical Analysis of Efficacy

The primary effectiveness analysis will consist of pair-wise comparison between each active treatment group and the vehicle treatment group, and between the two active treatment groups, based on the mean of per-subject percentages of target lesions judged to be clear on the PLA (PLA = 0) at Visit 8. To conduct this analysis, the percentage of each subject's target lesions judged to be clear on the PLA at Visit 8 will first be calculated for each subject. Then the analysis will calculate the mean of this parameter for each treatment group (yielding an estimate of the mean percentage of clear lesions across subjects), and an analysis of variance (ANOVA) model will be used to perform all pair-wise comparisons among the treatment groups. Pair-wise comparisons will be conducted on the least-squares means using the overall pooled error term of the model. All efficacy analyses will be based on the per protocol (PP) population, defined as all randomized subjects who completed the study with no major protocol violation.

A secondary effectiveness analysis will be conducted using the same methodology as the primary efficacy analysis based on the mean of per-subject percentages of target lesions judged to be clear or near-clear on the PLA (PLA \leq 1) at Visit 8. The primary and secondary analyses above will also be conducted separately for lesions in each body location, using the same methodology as specified above.

In addition to the above Visit 8 analyses, each of these analyses will be conducted at each other visit where PLA scores are collected, as exploratory analyses.

Three exploratory responder analyses will be conducted using the following criteria for classifying subjects as responders:

- Subjects with PLA = 0 for all 4 target lesions at Visit 8;
- Subjects with PLA = 0 for at least 3 target lesions at Visit 8; and
- Subjects with PLA \leq 1 for all 4 target lesions at Visit 8.

For each exploratory analysis, separate chi-square tests will be used to compare the percentage of responders between each active treatment group and the vehicle treatment group, and between the two active treatment groups. The chi-square analyses may be supplemented by one logistic regression model for each exploratory analysis that will allow all 3 pairwise comparisons to be performed within a single model.

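### Whether Site enters the primary ANOVA is left to an undefined, data-dependent criterion; if judged on the treatment p-value, 0.05 becomes about 0.06 to 0.07

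*Combined protocol and SAP*

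**What the plan says.** Section 12.2 defines the primary analysis as three pairwise comparisons of the mean per-subject percentage of clear target lesions at Visit 8. It states that "an analysis of variance (ANOVA) model will be used to perform all pair-wise comparisons among the treatment groups", using least-squares means and the model's pooled error term. The only statement about covariates closes the section: "ANOVAs will include Site in the model if doing so improves the sensitivity of the model for comparing treatment groups".

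The sentence just before it reads "For all analyses, two-tail alpha will be set to 0.05 with no adjustment for multiple comparisons". Section 12.1 likewise says "Two-tail alpha will be set to 0.05 for all comparisons".

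Nothing else in the document defines sensitivity in this sense, sets a cut-off, or says who decides, when, or with what knowledge of treatment. The synopsis describes the same ANOVA without mentioning Site. Section 7.2 gives the 1:2:2 ratio and names no stratification factor. Section 4.1 expects about 9 centers.

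**The concern.** The condition is tied to how well the model compares the arms, and that can only be judged once outcome data exist. On one natural reading, both models are fitted and the one that separates the arms better is kept. That gives the treatment comparison two chances to reach significance, and the reported p-value no longer comes from a single pre-specified model.

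The rule speaks of ANOVAs in the plural. It therefore reaches all three primary comparisons, the secondary analysis of clear or near-clear lesions, the body-location analyses and the analyses at other visits. Nothing requires the same choice in each. The comparison most exposed is 45% versus 40%, which is planned at about 85% power; the vehicle comparisons are planned at more than 95%.

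**Working it through.** **Inputs from the documents.** Arm sizes: "Fifty subjects will be randomized to the Vehicle treatment arm and 100 subjects will be randomized to each A-101 active treatment arm" (Synopsis). From section 12.1: "the expected standard deviation for the primary efficacy parameter is approximately 23.7" percentage points; "The mean difference between the two Active treatment groups is expected to be approximately 10 percentage points"; two-sided alpha 0.05. About 9 sites (section 4.1).

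**Input assumed.** The site share of outcome variance is not given, so it is varied from 0 to 20%.

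**Step 1: reproduce the plan's power.** The plan states "approximately 85% power for the comparison between the two Active treatment groups". The noncentrality is 10 / (23.7 × √(2/100)) = 10 / 3.352 = 2.984. Power is 84.7% by the normal approximation and 84.4% by the noncentral t. The stated figure reproduces.

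**Step 2: type I error for 45% versus 40%.** Simulated trials under the null had 50/100/100 subjects, SD 23.7, 9 sites of equal expected size and no stratification, with 20,000 trials per row. The simulation standard error is √(0.05 × 0.95 / 20,000) ≈ 0.0015. Each trial was analysed with and without Site.

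| Site share | Site never in | Site always in | Keep smaller p | Keep smaller SE | Keep smaller residual MS | Site F-test p<0.05 |
|---|---|---|---|---|---|---|
| 0 | 0.049 | 0.048 | 0.057 | 0.049 | 0.049 | 0.049 |
| 2% | 0.052 | 0.052 | 0.062 | 0.053 | 0.053 | 0.053 |
| 5% | 0.050 | 0.051 | 0.063 | 0.053 | 0.051 | 0.053 |
| 10% | 0.049 | 0.051 | 0.067 | 0.052 | 0.051 | 0.051 |
| 20% | 0.051 | 0.050 | 0.071 | 0.050 | 0.050 | 0.050 |

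A second simulation with unequal sites (5,000 trials per setting) gave 0.058 to 0.072 for the smaller p-value, 0.045 to 0.055 for the smaller SE or residual mean square, and 0.045 to 0.054 for either fixed model. With a five-level outcome (0, 25, 50, 75, 100%) and a 10% share, keeping the smaller p-value gave 0.064.

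**Step 3: dependence on balance.** With allocation balanced by site and a 10% share, keeping the smaller p-value gave 0.049. The inflation needs arms that are unevenly spread over sites.

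**Step 4: power if Site is always included.** The 8 degrees of freedom in themselves cost almost nothing: 84.4% with 247 or with 239. The larger cost is chance imbalance of arms across sites, which inflates the variance of the contrast by roughly 247/239 = 1.033. Against that, the residual variance falls by the site share s, so the noncentrality is about 2.984 / √((1 − s) × 1.033):

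- s = 0: 2.935, power about 83%
- s = 5%: 3.011, power about 85%
- s = 10%: 3.094, power about 87%

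Simulated power without versus with Site agrees to within about a point: about 84% versus 83%, 85% versus 84%, and 85% versus 87%.

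**The case against.** The sentence does not mention p-values or the observed difference. Section 12.2 bases the comparisons on the pooled error term, so a smaller error term is at least as natural a meaning of better sensitivity, and on that meaning the error rate stays at 0.05. This stands. A reader might infer that the model is chosen on the result and that 0.05 is not held. The documents do not support that as a flat statement: it is true on one of several readings.

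A reader might also infer that the choice is made after unblinding. The document gives no timing, so this is possible but not stated.

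The inflation also needs randomization that is not balanced by site. Section 7.2 states no stratification, but it does not rule it out. The upper end of the range needs a 20% site share, which is an assumption.

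The chance of any false positive over the three comparisons is 0.14 to 0.17 when the smaller p-value is kept. It would be wrong to charge all of that to the Site rule. About 0.12 arises with either fixed model, from the openly declared absence of multiplicity adjustment, which is a separate and larger matter.

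Finally, it is tempting to promise that including Site lifts power to about 86% or 88% at a 5% or 10% site share. Those figures assume arms perfectly balanced across sites, whereas the inflation arises only when they are not.

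What survives all this is that the plan does not say which reading applies, so it cannot show that it meets its own two-sided 0.05.

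**Conclusion.** The primary model depends on the data, through a criterion that is undefined and may be applied to the treatment result. Under the least favourable reading, with unstratified randomization and an assumed site share of 0 to 20%, the two-sided error rate for 45% versus 40% is about 0.058 to 0.072, at worst about 2 points above nominal. Under a criterion based on precision or on a Site F-test it is 0.05 to within simulation error or a few tenths of a point. With the model fixed in advance it is held, with or without Site. The harm is modest and conditional, but it concerns the primary analysis and is easily removed, so the sponsor should act.

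**What to change.** Replace the sentence on Site in section 12.2 with:

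> All ANOVAs will include treatment and Site as fixed effects; any pooling of small sites will be fixed before unblinding; the model without Site will be shown as a sensitivity analysis.

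Make the synopsis agree, and state in section 7.2 whether randomization is stratified by site. Fixing the model without Site, or giving a rule for Site that is blind to treatment, would also hold the error rate. Always including Site secures whatever precision there is to gain.

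The cost is one sentence and 8 of 247 error degrees of freedom. In power for 45% versus 40%, that is a loss of up to about 1 point if sites do not differ, about neutral at a 5% site share, and a gain of about 2 points at 10%.
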